5.3 PROTOCOL DEVIATIONS

A protocol deviation is defined as any departure from what is described in the protocol of a clinical trial approved by an Independent Ethics Committee (IEC)/Institutional Review Board (IRB) and Competent Authorities. Therefore, it applies to deviations related to patient inclusion and clinical procedures (e.g., assessments to be conducted or parameters to be determined), and also to other procedures described in the protocol that concern the Good Clinical Practice (GCP) guidelines or ethical issues (e.g., issues related to obtaining the patients' Informed Consent, data reporting, the responsibilities of the Investigator, etc.).

Deviations with no effects on the risk/benefit ratio of the clinical trial (such as minimal delays in assessments or visits) will be distinguished from those that might have an effect on this risk/benefit ratio, such as:

- Deviations that might affect the clinical trial objectives, such as those involving the inclusion/exclusion criteria (which could mean that the patient is not eligible for the trial) and those having an effect on patient evaluability.
- Deviations that might affect the patient's well-being and/or safety, such as an incorrect dosing of the study treatment due to not following dose adjustment specifications or an incorrect preparation of the medication.
- Deviations related to the following of GCP guidelines as described in the protocol and regulations in force, such as deviations when obtaining the Informed Consent or not following the terms established for reporting SAEs, etc.

No deviations that may have an effect on the risk/benefit ratio of the clinical trial will be authorized. All protocol deviations detected during the study will be appropriately documented, and those considered particularly relevant (i.e., those related to ethical issues, to fulfillment of GCP guidelines and with an effect on the risk/benefit ratio) will be notified, if applicable, to the pertinent IEC/IRB and to the Competent Authorities as established by local regulations.

5.4 REPLACEMENT OF PATIENTS

No patients will be replaced. For each group 1-3, all efficacy analyses will be done on Full Analysis Set (FAS) population (See [8.2.1 Full Analysis Set \(FAS\) population](#)).

Therefore, accrual in each group will end when the target number of evaluable patients in the FAS population has been reached.

5.5 PATIENT SCREENING

The Screening period starts once the patient has provided written informed consent and ends when the patient is randomised/enrolled in the study.

5.5.1 Screening Assessments and procedures

Parameters assessed during this time may serve as the baseline values (unless repeated before Day 1 treatment). The patient will be screened with the aim to complete screening within 24 h prior to administration of study treatment but allowing a maximum of 48 h prior to administration of study treatment if required. Upon confirmation of eligibility, the patient will be randomised and start treatment on the same day.

	PROCEDURES / ASSESSMENTS
Patient Registration	
ICF signature.
Demographics	
Demographic data: gender, year of birth, age and race, according to the local regulation.
Medical and immunodeficiency history.	
Medical HistoryUnderlying disease causing immune deficiency.Concomitant therapies.SARS-CoV-2 Vaccination status (brand and dates of vaccines)Prior medications for COVID-19.Scheduled therapies for the underlying disease and compliance. 
A detailed history of medications and procedures will be documented for each patient at screening.
 
Any of the medications ongoing before the first dose of the study treatment will be recorded, including start/stop dates, indication, dose and frequency.
 
Specific focus will be done on medications used to treat COVID-19 or the underlying disease, including the theoretical schedule for next coming administrations

PROCEDURES / ASSESSMENTS	
Clinical evaluation	
 COVID-19-related signs and symptoms checklist (Appendix 10 - COVID-19 signs/symptoms checklist) and need for hospitalisation. Complete physical examination. Height in centimetres (cm) will be measured at screening. Body weight will be measured in kilograms (kg). Body mass index will be calculated. A full physical examination will be performed and should include general appearance, skin, neck, eyes, throat, lungs, heart, abdomen, back, lymph nodes, extremities, and neurological examinations, including Glasgow score (See Appendix 11 – Glasgow Coma Scale). Clinical status (11-point WHO Clinical Progression Scale) Vital signs will include body temperature (°C), SBP (mmHg), DBP (mmHg), pulse rate (bpm) and respiratory rate (breaths/min). Lung function tests include partial pressure of oxygen (PaO₂), fraction of inspired oxygen (FiO₂) and oxygen saturation (SpO₂). PaO₂/FiO₂ ratio will also be measured; either Ellis or Rice formulae can be used to estimate PaO₂/FiO₂ ratio (Appendix 5 - Imputation of PaO₂/FiO₂ ratio).
Detection of SARS-CoV-2	
 qRT-PCR SARS-CoV-2 or SARS-CoV-2 Rapid Antigen Test (RAT) 
Documented diagnosis of SARS-CoV-2 infection, determined by a regulatory approved test, collected no more than 3 days prior to study randomisation, with either a Ct value ≤30 or a positive antigen test.
 
SARS-CoV-2 variant will be documented at any time during the study, if available information exists.

Minimum set of laboratory tests for screening (at site's laboratory)	
Haematology: differential white blood cells (WBC) counts (including neutrophil and lymphocyte counts), platelet count (See Appendix 8 – Clinical Laboratory Analyses).
 
Biochemistry: Liver function test (ALT, total bilirubin (direct bilirubin if total is abnormally elevated), calculated CrCL [as per Chronic Kidney Disease Epidemiology Collaboration (CKD-

	PROCEDURES / ASSESSMENTS
	EPI)], C-reactive protein (CRP), blood urea nitrogen (BUN)/urea (See Appendix 8 – Clinical Laboratory Analyses).
ECG	A 12-lead ECG will be performed in triplicate. Cardiac rhythm will be identified in ECG intervals of at least 30 seconds of duration. PR interval, QT interval (raw and QTcF), heart rate and QRS complex, with specialist assessment/judgment of further evaluation if appropriate.
Pregnancy test (if patient is a WOCBP)	A urine or serum pregnancy test will be performed for female patients of childbearing potential (i.e., female patients who are not postmenopausal or surgically sterile) at screening.
Eligibility assessment	Documented review of all Inclusion and Exclusion criteria.
ISARIC-4C mortality score	Appendix 4
Adverse events	AEs that occurred after signature of the informed consent form will be reported.

The patient will be a screening failure if not all inclusion criteria are met or if any exclusion criterion is met. A patient should only be treated if eligibility criteria are still met according to assessments performed closest to first drug administration.

5.6 PATIENT RANDOMISATION

Patients will be sequentially allocated in their respective group, following the algorithm depicted in [Figure 9](#).

Central randomisation will be implemented. In groups 1-3, patients will be assigned to the experimental or the control arms at a 1:1 ratio. Stratification will be performed in the randomised groups. The ISARIC-4C mortality score will be used as a stratification factor in all groups (score <9/≥9). In addition, the type of graft (allogeneic haematopoietic/lung or intestinal/other) will be used for Group 1, whereas the underlying disease will be considered for Groups 2 and 3. For Group 2, the factor categories will be haematological neoplasm vs other disease; the respective categories for Group 3 will be neoplasia vs other. Stratification is not applicable in the non-randomised Group 4.

Day 1 is defined as the day of randomisation. Treatment must start within the same natural day.

5.7 EVALUATIONS AND PROCEDURES DURING TREATMENT

	ASSESSMENT/PROCEDURES	TIME
Clinical evaluation	
 COVID-19-related signs and symptoms checklist (Appendix 10 – COVID-19 signs/symptoms checklist). Clinical status (11-point WHO Clinical Progression Scale). Vital signs will include body temperature (°C), SBP (mmHg), DBP (mmHg), pulse rate (bpm) and respiratory rate (breaths/min). Targeted physical examination. A targeted physical examination will include heart, lungs, abdomen, extremities plus central nervous system (CNS) assessment, based on the investigator's decision as per clinical evolution. Lung function tests include PaO₂, FiO₂ and SpO₂. PaO₂/FiO₂ ratio will also be measured; either Ellis or Rice formulae can be used to estimate PaO₂/FiO₂ ratio (Appendix 5 - Imputation of PaO₂/FiO₂ ratio). 	Days 1, 2, 3, 4 (± 1). When applicable, these assessments should be performed before treatment administration.

	ASSESSMENT/PROCEDURES	TIME
	
 • Concomitant therapies. • Subsequent medications for SARS-CoV-2 infection. • Subsequent medications for the underlying disease. 	Days 1, 2, 3, 4.
Laboratory tests*	Haematology: haematocrit, red blood cells (RBC), differential WBC counts (including neutrophil and lymphocyte counts), platelet count and haemoglobin (See Appendix 8 – Clinical Laboratory Analyses).	Days 1, 4 (± 1), and whenever clinically indicated for an AE evaluation. When applicable, these assessments should be performed before treatment administration.
	Biochemistry: Liver function test [ALT, AP, AST [†] , albumin, total bilirubin (direct bilirubin if total is abnormally elevated)], lactate dehydrogenase (LDH), glucose [fasting], sodium, potassium, calcium, BUN/urea, gamma glutamyl transferase (GGT), creatinine, calculated creatine clearance [CKD-EPI], creatine phosphokinase (CPK), amylase, lipase, procalcitonin, ferritin, and CRP (See Appendix 8 – Clinical Laboratory Analyses).	Days 1, 4 (± 1), and whenever clinically indicated for an AE evaluation. When applicable, these assessments should be performed before treatment administration.
	Coagulation: D-Dimer (See Appendix 8 – Clinical Laboratory Analyses).	Day 1, 4 (± 1), and whenever clinically indicated for AE evaluation. When applicable, these assessments should be performed before treatment administration.
	Urine analysis (semi-quantitative elemental tests	Day 1 (previous to treatment administration). Repeat whenever

	ASSESSMENT/PROCEDURES	TIME
	for specific gravity, blood, pH, proteins, bilirubin, glucose, ketones, nitrites, and qualitative analysis of the sediment).	clinically indicated for AE evaluation. When applicable, these assessments should be performed before treatment administration.
Inflammatory and immunological biomarkers in blood (central laboratory)	Luminex® Multiplex cytokine assessment.	Days 1, 2, 4 (± 1).
Anti-SARS-CoV-2 (central laboratory)	IgG/M anti-protein S and N.	Day 1 previous to treatment administration.
	T-cell response (IFN- γ) to SARS-CoV-2 S-protein (Quantiferon®).	
Detection of SARS-CoV-2	qRT-PCR in oro/naso-pharyngeal exudates (central laboratory).	Day 1, 4 (± 1).
	Rapid Antigen Test (at site).	Day 1, 4 (± 1).
ECG**	Cardiac rhythm will be identified in ECG intervals of at least 30 seconds of duration, PR interval, QT interval (raw), heart rate and QRS complex, with specialist assessment/judgment of further evaluation if appropriate.	At screening or Day 1 (previous to treatment administration). Repeat on Day 4 (± 1), and whenever clinically indicated for AE evaluation.
Chest X-ray	Qualitative evaluation and Brixia score (See Appendix 9 – Brixia Score). (Submission to central review)	At screening or Day 1 (previous to treatment administration). Repeat whenever clinically indicated for AE evaluation.
ISARIC-4C deterioration score	Appendix 4	At screening or Day 1 (previous to treatment administration).
Pharmacokinetics (central laboratory)	(See details in Section 7.6).	Days 1, 3, 4 (see details in Section 7.6).
Antiviral Treatment administration	(See details in Section 6.1).	Days 1-3 in the experimental arm.⁹

	ASSESSMENT/PROCEDURES	TIME
		From Day 1 (date of randomisation) to the last dose of the antiviral therapy in the control arm. [¥]
Survival status		Throughout the treatment period.
Hospitalisation status		Throughout the treatment period.
Adverse events	As per NCI-CTCAE v.5***	Throughout the treatment period.

* Central laboratory for all the tests, except for screening.

** Triplicate.

*** The “AE form” will be used to report signs and symptoms and medical history in case of any significant change (improvement or worsening) during the study, as well as for events that occur after the first drug infusion or any event related to a study procedure within the study period (according to ICH guidelines).

[¥]Antiviral treatment period in both arms will end 24 h after administration of the last dose of the antiviral therapy. If no antiviral was given in the control arm, then the treatment period will finish on Day 4.

[†]See [Section 7.2.1 Adverse Events of Special Interest \(AESIs\)](#).

For patients included in the study (all randomised patients) but never treated, only the applicable forms at baseline and off-study visit modules of the e-CRF should be completed but SAEs occurring during screening period need to be reported (using paper SAE forms).

All cases of treatment discontinuation must be documented (date and reason) in the electronic case report form (eCRF). A subject may stop the study treatment but desirably should continue follow-up to the end of study.

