	ASSESSMENT/PROCEDURES	TIME
Detection of SARS-CoV-2	qRT-PCR in oro/naso-pharyngeal exudates (central laboratory).	Day 8 ± 1 Day 15 ± 1 Day 30 ± 2 Day 45 ± 2
	Rapid Antigen Test (at site).	Every other day while admitted, Day 8 ± 1 Day 15 ± 1 Day 30 ± 2 Day 45 ± 2
ECG**	Cardiac rhythm will be identified in ECG intervals of at least 30 seconds of duration, PR interval, QT interval (raw), heart rate and QRS complex, with specialist assessment/judgment of further evaluation if appropriate.	Whenever clinically indicated for AE evaluation.
Chest X-ray	Qualitative evaluation and Brixia score (See Appendix 9 – Brixia Score). (Submission to central review)	Day 15 ± 1 Day 30 ± 2
Pharmacokinetics (central laboratory)	(See details in Section 7.6).	Day 8 (±1) (see details in Section 7.6).
Survival status		Throughout the treatment period
Hospitalisation status		Throughout the treatment period
Adverse events	As per NCI-CTCAE v.5***	Throughout the treatment period.

* Central laboratory for all the tests

** Triplicate.

*** The “AE form” will be used to report signs and symptoms and medical history in case of any significant change (improvement or worsening) during the study, as well as for events that occur after the first drug infusion or any event related to a study procedure within the study period (according to ICH guidelines).

¹See [Section 7.2.1 Adverse Events of Special Interest \(AESIs\)](#).

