6.1.4 Treatment Schedule and Dose

Plitidepsin will be administered as a 60-min (±5 min) IV infusion, every 24 h (±30 min)* for 3 consecutive days, at a dose of 2.5 mg.

For prevention of infusion-related (i.e., plitidepsin-related) reactions (IRRs), allergic reactions and emesis reactions, administration of premedications is mandatory in the experimental arms.

*Treatment windows do not apply for the first 30 patients enrolled in this study (experimental arm) who will be included in the pharmacokinetics evaluations.

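### The Day 4 (±1) window includes dosing Day 3, so the only scheduled post-baseline ECG can precede the third infusion and still be summarised as Day 4

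*Protocol*

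**What the plan says.** **Dosing.** Protocol Section 5.6: "Day 1 is defined as the day of randomisation. Treatment must start within the same natural day". Section 6.1.4 gives plitidepsin every 24 h (±30 min) "for 3 consecutive days, at a dose of 2.5 mg", and the Section 5.7 table lists administration as "Days 1-3 in the experimental arm". The third infusion is therefore on Day 3.

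**ECG.** The baseline tracing in Section 5.7 is "At screening or Day 1 (previous to treatment administration"). The repeat is "Repeat on Day 4 (± 1), and whenever clinically indicated for AE evaluation". In follow-up (Section 5.8) the entry is "Whenever clinically indicated for AE evaluation", and Section 5.9 likewise asks for an end-of-study ECG only on clinical grounds.

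**Laboratory tests.** For haematology and biochemistry Section 5.7 says "Days 1, 4 (± 1), and whenever clinically indicated for an AE evaluation. When applicable, these assessments should be performed before treatment administration". The D-dimer entry is equivalent. The qRT-PCR and rapid antigen rows use the same Day 4 (±1) window without the pre-dose instruction.

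**Analysis.** SAP Section 9.0 keeps the protocol's assessment windows and refers to protocol Appendix 13 for trial days. SAP Section 11.9 summarises ECGs and their changes from baseline by visit. SAP Section 11.7 reports laboratory data by worst grade and shift table. No SAP rule relates a Day 4 record to the last infusion.

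**The concern.** A Day 4 safety assessment in a three-day course should describe the patient after the whole course. The window as written also admits a record taken after only two infusions, and such a record complies fully with the protocol.

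This matters most for the ECG, because no other tracing is planned after dosing starts and cardiac events are adverse events of special interest (protocol Section 7.2.1). An early tracing leaves no planned look at the effect of the full course in that patient. The by-visit ECG table would then combine values after two infusions with values after three under one label. The Day 4 changes in viral load and inflammatory markers are exposed to the same mixing, although there the cost is a blurred visit rather than a lost one, since those measures are repeated later.

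**Working it through.** The plan gives no figure to reproduce, so the check compares calendar days and hours.

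**1. Overlap**
- Window: 4 − 1 = 3 to 4 + 1 = 5, so Days 3, 4 and 5.
- Dosing days: 1, 2 and 3.
- Common day: Day 3.

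**2. Day numbering against protocol Table 3 (PK samples)**
- The third infusion starts at 48 h and ends at 49 h, on Day 3.
- End of infusion plus 3, 6, 23 and 119 h gives 52, 55, 72 and 168 h. All four match the table.
- The Day 4 PK sample is thus tied to the end of the third infusion (23 h after it, ±4 h). The Day 4 ECG and laboratory tests have no such tie.

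**3. Exposure at a Day 3 pre-infusion record**
- 2 × 2.5 mg = 5.0 mg; full course 3 × 2.5 mg = 7.5 mg; 5.0 / 7.5 = 67%.

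**4. How wide the Day 4 label is**
- With two intervals of 24 h ± 0.5 h, the third infusion starts 48 ± 1 h after the first, that is at 47 to 49 h. (Section 6.1.4 exempts the PK patients from the dosing tolerances; Table 3 places their third infusion at 48 h.)
- Assumption, because clock times are not given: the first infusion starts at hour h of the day, with h between 8 and 20.
- Part of Day 3 before the third infusion: h hours. Share of the 72 h window: h / 72.
- Latest in-window time after the end of the third infusion: 120 − h − 49 hours.

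| First infusion | Window time before third infusion | Latest time after third infusion |
|---|---|---|
| 08:00 | 8 / 72 = 11% | 120 − 8 − 49 = 63 h |
| 20:00 | 20 / 72 = 28% | 120 − 20 − 49 = 51 h |

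The percentages are shares of window time, not of patients. They show that one label can run from before the third infusion to more than two days after it.

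**5. What each row of Section 5.7 asks for on Day 3**
- Laboratory tests: "When applicable, these assessments should be performed before treatment administration". For a plitidepsin patient sampled on Day 3, this directs the draw to precede the infusion.
- ECG: the pre-treatment condition belongs to the baseline tracing only. A Day 3 repeat may be done before or after the infusion.
- qRT-PCR and rapid antigen test: either side of the infusion is allowed.

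**6. Later planned measurements**
- ECG: none.
- Laboratory tests: Days 15 and 30 in Section 5.8 (the timing cell is broken in the text and may list more), with Day 8 named for several analytes in Section 3.3.3, and Day 60 in Section 5.9.

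**The case against.** Several points on the other side are sound.

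- **Appendix 13.** The SAP sentence on windows refers to this schedule, which is not among the pages reviewed. A footnote there could tie Day 4 to the last infusion. This stands as a limit; if such a footnote exists, Section 5.7 should agree with it.
- **A Day 3 ECG need not be early.** A reader might infer that every patient assessed on Day 3 lacks a tracing after the full course. The documents do not support that, since a patient present for the third infusion may have the ECG afterwards. Only tracings taken before it are affected.
- **Laboratory reporting.** A reader might infer that the safety laboratory tables also mix two-dose and three-dose values by visit. SAP Section 11.7 specifies worst grade and shift tables, which do not depend on the Day 4 label, and laboratory tests recur. Transaminases above the Section 7.2.1 threshold also trigger repeat testing.
- **Not purely a one-arm problem.** Control antivirals have no fixed length, so control Day 4 values can also fall during or after treatment. The overlap with the third infusion is specific to plitidepsin, but it would be wrong to say that only that arm has mixed treatment states.
- **No formal contradiction.** A Day 3 assessment lies inside the treatment period. The lower end of the window may be no more than a tolerance.
- **Early closure.** The study was stopped for low recruitment and the SAP now plans descriptive output only, so changing a site window does little for this trial.

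Together these narrow the point to the ECG and to how early records are labelled. They do not remove it: nothing in Section 5.7 prevents a pre-infusion Day 3 tracing, and no later ECG is planned.

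**Conclusion.** The concern holds in a limited form. On the text available, the only scheduled post-baseline ECG can be taken after 67% of the course, leave that patient with no planned tracing after the full course, and be reported as Day 4. A Day 3 laboratory draw is directed to be pre-dose, but the consequence is smaller because later draws are planned and the main tables do not use the visit label. Day 4 viral-load and biomarker changes carry the same labelling risk in exploratory, descriptive summaries.

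The number of patients affected cannot be derived from the documents and may be small or zero. In a trial closed early with few patients, however, one or two early records can move a by-visit summary. The conclusion assumes that Appendix 13 does not narrow the window. This is an inexpensive improvement to safety capture and labelling; it does not undermine the trial's conclusions.

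**What to change.** **Protocol (for consistency, and for any reuse of the design).** Reconcile the Day 4 window in Section 5.7 with the dosing days, and check Appendix 13 for the same wording. Either require the Day 4 ECG and laboratory tests after the end of the third infusion in the experimental arm, or set the window to Day 4 (0/+1) with the same calendar window in the control arm. Limit the pre-dose instruction for laboratory tests to Day 1.

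**SAP (the part that still changes this trial's output).** Add to Section 9.0 that, in the plitidepsin arm, a Day 4 record taken before the third infusion is treated as unscheduled. Keep it in worst-grade tables and listings, and leave it out of the Day 4 by-visit and change-from-baseline summaries for ECG, viral load and biomarkers. A patient who never receives a third infusion keeps the Day 4 record, provided it follows the last infusion given. The rule needs the clock times of the assessment and the infusion; where the assessment time is missing for a Day 3 record, flag it in the listing as undetermined. Report how many records the rule moves, which also gives the size of the problem.

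**Cost.** One schedule entry and a short SAP paragraph. Sites lose one day of flexibility: a patient leaving on Day 3 would be assessed after that day's infusion, or return on Day 4 or 5 (under the (0/+1) window, only the return is open). The Day 4 summaries may contain a few fewer values. No safety observation is discarded.
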